The remaining specimen will be delivered to Wisconsin Diagnostic Labs (Milwaukee, Wisconsin) which uses the COBAS 4800 system for cytology reading. Cytology findings will use the Bethesda System³⁹ with classification as follows: negative for intraepithelial lesions; atypical squamous cells of undetermined significance (ASCUS) or atypical squamous cells, cannot rule out high-grade squamous intraepithelial lesion; low-grade squamous intraepithelial lesion; or high-grade squamous intraepithelial lesion. Reflex HPV testing will be conducted for all abnormal (i.e., \geq ASCUS) specimens.

Anal cytology is approved for use in anal cancer screening. Thus, individuals will be given the cytopathology results (either abnormal, normal, or inadequate/unsatisfactory) and any HPV reflex testing results through the individual's preferred mode of communication; however, regardless of the result, all individuals will be encouraged to seek medical advice about their results. Currently, there is no FDA approval for anal self-sampling, thus, the cytology results should not be used to guide care or referrals.

The 0.5 mL aliquot will be batch-shipped to the Moffitt Cancer Center for HPV genotyping. Moffitt will extract DNA from the 0.5 mL aliquot (MDx Media Kit, QIAGEN) and then use the SPH₁₀-LiPA₂₅ kit according to the manufacturer's instructions to first test for adequacy of the specimen, defined by the presence of human RNase P, and second to test for HPV DNA, and HPV genotypes.³⁴

HPV genotyping results from Moffitt will not be available for several months after the cytology screening since the specimens will be batched shipped only after all 60 individuals complete the screening. In addition, participants with abnormal cytology results will also have HPV reflex testing which would indicate if a high-risk HPV type is detected in the cytology specimen. Thus, the results of the HPV genotyping will not be provided to the participant after genotyping is completed and results are available.

F.5 Subject Withdrawal Criteria

F.5.1 Subject-initiated Withdrawal

A participant may decide to withdraw from the study at any time.

F.5.2 Investigator-initiated Withdrawal

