The investigator may withdraw a participant whenever continued participation is no longer in their best interests. Reasons for withdrawing a participant include, but are not limited to, a participant's noncompliance, or simply significant uncertainty on the part of the investigator that continued participation is prudent.

F.5.3 Replacement Policy and Data Usage

[figure not shown]
Individuals who sign the informed consent form and are randomized, but subsequently withdraw, will be replaced. Data collected from individuals that withdraw or discontinue from the study will be used.

F.6 End of Pilot Study Definition

An individual is considered to have completed the study if they have completed the post-cytology survey. Those who participated in the pilot study will not be eligible or involved in the parent SOLO study.

G Pilot Study Team, Assessments, and Procedures

G.1 Pilot Study Team Structure

G.2 Pilot Study Schedule of Events

Procedures and Events	Recruitment	Consent & Cytology Appointment	End of Pilot Study
Eligibility Screening	X		
Informed Consent		X	
Randomization and Enrollment ¹		X	
INTERVENTION			
Self-sampling with a 5 cm nylon-flocked swab		X	
CONTROL			
Self-sampling with a 3 cm nylon-flocked swab		X	
RESEARCH PROCEDURES			
Adverse Events Collection ²	(SAEs only)	AEs collected from the start of the intervention to 30 days after the end of the intervention	
Cytology Appointment Computer-Assisted Self-Interview (CASI) ³			X

¹ After an individual has signed the informed consent form and been randomized to one of the study arms, they are considered enrolled in the study.

² Refer to Section 7.2 for adverse event (AE) collection and reporting requirements.

³ The cytology CASI will be given to participants immediately after they complete cytology collection.

G.3 Pilot Study Procedures to be Conducted by Site

Activity	Milwaukee		Tampa
	Medical College of Wisconsin	Wisconsin Diagnostic Labs	Moffitt Cancer Center
Funding	Primary Award	Service contract	Service contract
Recruitment	X	-	-
Consenting	X	-	-
Randomization	X	-	-
Participant interaction	X	-	-
Obtaining PHI	X	-	-
Surveying	X	-	-
Access to PHI	X	X	-
Supplying cytology kits	X	-	-
Cytology reading	-	X	-
HPV genotyping	-	-	X

Activity	Milwaukee		Tampa
	Medical College of Wisconsin	Wisconsin Diagnostic Labs	Moffitt Cancer Center
Key personnel	X	-	-

H Statistical and Epidemiological Considerations

H.1 Pilot Study Primary Endpoints

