The study investigator will be responsible for determining whether an AE is expected or unexpected as indicated in the protocol. An AE will be considered unexpected if the nature, severity, or frequency of the event is not consistent with the risk information previously described for the study intervention.

I.3 Collection and Reporting Requirements for Adverse and Serious Adverse Events

AEs that are Grade 3 or higher and are related (possibly, probably, or definitely) to the intervention will be collected from the time the subject starts the intervention through conclusion of the intervention, which comprises the cytology self-sampling and CASI. AEs will be tracked and followed until resolution, the subject withdraws consent or is lost to follow-up (including individuals who discontinue early). SAEs that occur after the subject has signed the consent form through 30 days after the conclusion of the intervention will be collected. Adverse events collected per the protocol should be followed with appropriate medical management.

AEs will be collected as reported. In the case of an adverse event, participants will be instructed to contact study staff and/or investigators as soon as possible, ideally within 24 hours. All Grade 3 and higher adverse events will be discussed with the PI and appropriate study staff. The PI will oversee that all AEs, SAEs, and UPIRSOs, are reported appropriately. Information about adverse events experienced by study individuals will be monitored by the following means:

- Report given by study participants to study staff, either in person or by telephone.
- Report given to study staff by study participants' family or friends, either in person or by telephone.
- Report by the participant's physician or other health care provider involved in the subject's care.
- Report from a hospital or other healthcare facility where the study participant is being treated for the serious adverse event.
- Other persons who may have knowledge of such a serious adverse event.

The PI will consult with other investigator(s) to assign event attribution category (unrelated, unlikely, possible, probable, or definite).

I.4 Institutional

Adverse and serious adverse events are not expected. If such events occur, AEs and SAEs will be reported per MCW Institutional Review Board (IRB) guidelines and the MCWCC Data and Safety Monitoring Plan (DSMP).

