The study team, including the PI, study coordinator, and other study staff will have weekly meetings. At each weekly meeting after enrollment starts, the study coordinator will provide the following information: number of participants entering the pilot study and completing cytology self-sampling, the number of dropouts, and reasons for dropout. Information about any adverse events also will be presented, including potential anxiety from cytology results. These participants will be managed using standard-of-care practices. By examining this information, the team will keep abreast of critical issues regarding reconsenting and data integrity.

- *Participant Records*. The computer-assisted self-interviews themselves will be identified only by ID number and do not contain personal identification information. Information linking the participants' identity to the study data will be kept on password-protected secure servers, while signed ICFs will be archived separately at the Medical College of Wisconsin.
- *Computer records*. Passwords and dual authentication will be used to limit access to computer records and pilot study data. No information that could lead to personal identification of participants will be included in any of the reports or given to any non-authorized person.

All raw data, data figures, data interpretation, models, and conclusions drawn from this pilot study will be managed by the principal investigator. The findings from this study may be presented at relevant conferences/meetings, published in a respectable peer-reviewed journal, or used as preliminary data in a grant application to justify extramural funding.

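### Sections G.2 and I.3 set different collection windows for non-serious adverse events (30 days against the end of the visit), and the footnote linking them cites a section that does not exist

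*Combined protocol and SAP*

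**What the plan says.** Section I.3 limits non-serious AE collection to events of Grade 3 or higher judged at least possibly related to the intervention. Collection starts when the intervention starts and runs "through conclusion of the intervention, which comprises the cytology self-sampling and CASI". The same section collects serious adverse events (SAEs) from consent to 30 days after the intervention.

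The G.2 Schedule of Events has a different entry: "AEs collected from the start of the intervention to 30 days after the end of the intervention". Its footnote 2 reads "Refer to Section 7.2 for adverse event (AE) collection and reporting requirements".

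Section L says of the weekly team meeting: "Information about any adverse events also will be presented, including potential anxiety from cytology results". It adds: "These participants will be managed using standard-of-care practices".

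Section F.4 governs what participants hear after the visit: "individuals will be given the cytopathology results (either abnormal, normal, or inadequate/unsatisfactory"), together with any reflex HPV result. It also says "regardless of the result, all individuals will be encouraged to seek medical advice about their results", and then: "Currently, there is no FDA approval for anal self-sampling, thus, the cytology results should not be used to guide care or referrals".

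**The concern.** Two operative parts of the protocol give different stopping points for the same data. Under I.3, a related, non-serious Grade 3 event that begins after the participant leaves is outside collection. Examples are delayed bleeding, pain or infection, or severe anxiety once a cytology result arrives. Under G.2 the same event is inside collection for 30 days.

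Two outputs rest on this. H.3.1 tabulates AE frequencies in each arm, and the arms differ in insertion depth, so delayed local events are part of what that table should show. Table 1 sends related Grade 3 and 4 AEs to the Data Safety and Monitoring Committee, with unexpected ones due within 5 calendar days. An event that is never collected reaches neither.

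**Working it through.** The plan gives no figure of its own on this point. The check compares the sections and adds simple arithmetic.

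**Step 1: when does the I.3 window close?** I.3 defines the intervention as the self-sampling plus the CASI (the survey). F.3 and G.2 footnote 3 place the CASI immediately after sampling. The Protocol Summary puts participation at about 30 minutes. Collection of non-serious AEs after the visit is therefore 0 days.

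**Step 2: the windows side by side.**

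| Event type | I.3 | G.2 |
|---|---|---|
| Non-serious AE, days after the intervention | 0 | 30 |
| SAE, days after the intervention | 30 | no separate end point stated |

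Difference for non-serious AEs: 30 − 0 = 30 days per participant. With 60 participants (section D): 60 × 30 = 1,800 participant-days observed under one section and not under the other. This measures observation time. It is not a count of events.

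**Step 3: does the cross-reference settle it?** Footnote 2 cites Section 7.2. The sections are lettered A to L, so there is none. The nearest match by number, I.7.2, concerns protocol deviations. By subject the footnote describes I.3, and I.3 is the section it disagrees with. Nothing says which prevails.

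**Step 4: trace one event.** Take a related, unexpected, non-serious Grade 3 event on the day after swabbing.

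- Following G.2: collected, counted in H.3.1, and sent to the committee within 5 calendar days under Table 1.
- Following I.3: not collected, not counted, and not sent under Table 1. I.3's follow-up to resolution does not help, because it applies to AEs already collected.
- If the event were serious: collected, because I.3 takes SAEs to 30 days.

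**Step 5: result-related anxiety.** F.3 and F.4 send the vial to the Tissue Bank and then to the laboratory after the visit. No cytology result can exist when the I.3 window closes. This is an inference, since no turnaround is stated, but a secure one. Under a 30-day window the days left after delivery on day *d* are 30 − *d*. For assumed deliveries on days 7, 14, 21 and 30 this gives 23, 16, 9 and 0.

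**The case against.** The strongest reply is that little is left uncovered. SAEs, including medically important events, are collected to 30 days. I.5 sends unexpected, related problems suggesting greater physical or psychological harm to the IRB within five calendar days, with no limit tied to the CASI. I.4 expects no AEs. All of this stands, and it is why the point is minor.

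A second reply is that footnote 2 names its subject, so a careful reader will find I.3 despite the wrong number. That is fair as to the target. But arriving at I.3 only exposes the conflict, because the schedule that staff work from still says 30 days.

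A third reply is that section L describes what a meeting hears and sets no collection window. This also stands. L conflicts with I.3 only by implication: it expects result-related anxiety among the AE information, yet I.3 stops before a result exists. The direct conflict is between G.2 and I.3.

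A reader might go further and infer that F.4 contradicts itself, or leaves participants with abnormal cytology without direction. The documents do not support that. An unapproved self-collected sample should not direct care, and advising everyone to ask a clinician is consistent with that limit. Reflex HPV results are returned with the cytology category for specimens at ASCUS or worse. F.4 does not say whether participants hear the restriction. The consent pages are not available and no result letter is included, so what participants are told cannot be checked. Giving coarse categories with the same advice to everyone is a defensible way to honour the restriction.

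**Conclusion.** The conflict is real and of minor severity. For non-serious, related AEs of Grade 3 or higher, the plan gives both 0 and 30 days of collection after the visit, and the cross-reference cannot resolve it. The by-arm AE table and part of the committee reporting depend on the section chosen. The primary endpoints are unaffected.

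How many events would be lost cannot be stated. The plan gives no AE rate, and the 1,800 participant-days say nothing about frequency. The conclusion rests on the text of G.2 and I.3 alone and needs no assumed abnormality rate or turnaround time.

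It does not extend to F.4. Naming the Bethesda category, setting contact attempts or adding a confirmation script are optional suggestions. Acting only on abnormal results would also strain against F.4's own restriction on using them.

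**What to change.** In I.3, keep the grade and relatedness limits and the start point, and replace the end point for non-serious AEs with 30 days after the conclusion of the intervention. This matches G.2 and the SAE window already in I.3. In G.2, change footnote 2 to cite Section I.3. Shortening G.2 to match I.3 would also remove the conflict, but it would leave every non-serious event after the visit uncollected.

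One limit should be understood. I.3 defines the intervention as sampling plus the CASI, so whether anxiety from a result counts as related stays an attribution judgement for the investigator. An onset after day 30 would still fall outside.

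Cost: one IRB-approved amendment under K.8 and slightly more AE record-keeping. I.3 collects AEs as they are reported, so no visits are added. The SAE window already runs to 30 days, so the study is not lengthened: about 2 months of accrual plus 30 days is about 3 months, inside the 4 months in section D.

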An important component of SOLO is the testing of two different kinds of swabs, nylon-flocked and Dacron, for molecular and cytological adequacy and end user acceptability within a self-sampling and clinician-sampling context. We chose a nylon-flocked (NF) swab for use in SOLO given its high adequacy in our prior study: the Prevent Anal Cancer (PAC) Self-Swab Study (R01 CA215403, PI: [name]); however, this NF swab is unlikely to be available for clinical use in the future due to recent changes in the manufacturer's priorities. Since SOLO results need to be widely generalizable and relevant to anal cancer screening, we need to use a different NF swab model and assess its cytological and molecular performance characteristics in a pilot study before beginning SOLO. Given our prior success with a NF swab developed by Copan Italia s.p.a. (Brescia, Italy) we will test the feasibility of a new Copan swab developed for anal cancer screening.

We will test the cytological performance of the swab at two insertion depths, 3 cm and 5 cm, to determine which insertion depth is better at collecting cells from the squamocolumnar junction (SCJ), an anatomic site that is particularly vulnerable to carcinogenic transformation. We hypothesize that the 5 cm insertion will result in a higher quality specimen with cells from the SCJ. However, the deeper swab insertion may affect end user acceptability without increasing adequacy or quality.

We will test the new swab with 60 individuals who were participants in the PAC Self-Swab Study and who agreed be contacted for follow-up studies. Individuals will be randomized to use the new NF swab with either a 3 cm or 5 cm insertion depth. After consenting, individuals will receive written instructions and then conduct the self-sampling in private. Staff will take the swab in PreservCyt to the Medical College of Wisconsin Tissue Bank where it will be aliquoted for assessment of cytology and reflex HIV testing at Wisconsin Diagnostic Labs and HPV genotype at Moffitt Cancer Center. We have one objective: To ensure the use of a swab in SOLO that is comparable to the originally proposed swab for SOLO, determine the preliminary performance characteristics of the new NF swab. We have three hypotheses within the objective:

- **H1:** A higher proportion of the new NF swabs with 5 cm insertion will have SCJ cells compared to the NF swab for 3 cm insertion.

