Potential participants will be screened using an online computer-assisted self-interview (CASI). Those who are eligible will be asked to leave contact information. Study staff will contact eligible individuals, provide an overview of the pilot study, and invite the individual to a schedule a consenting session which will be followed by the cytology screening at the Curative Building on the MCW campus. Those who are not eligible will be thanked for their interest and provided links to vetted anal cancer education websites. Minimal Protected Health Information (PHI) will be collected in the eligibility survey.

At the consenting session staff will first ask the eligible individual to confirm their email address, name, and birthdate. The session will occur in a closed office and include information about 1) high rates of anal cancer in SGM, 2) anal cancer screening and the role of swabbing, 3) pilot study activities, and 4) the potential harms and benefits of participation. The staff member obtaining consent will emphasize that participation is voluntary and that participants can choose to join and,

if desired, leave the pilot study at any point without any repercussions. The ICF will also notify individuals that we will collect their street address to support payment using the MCW visa card.

Prior to obtaining their signature, the staff member will ask the individual if they have any questions and, if not, to briefly review their understanding of their participation by asking simple questions about the pilot study to be sure the information was clearly understood.

Individuals agreeing to provide consent will sign an ICF hard copy. It will be photocopied with the copy given to the participant.

F Pilot Study Design and Intervention

F.1 Study Design

This pilot feasibility study will use a randomized controlled trial design.

Figure 1 illustrates the pilot study design.

F.2 Randomization

Consented individuals will be randomized to either the intervention (5 cm insertion depth) or the control (3 cm insertion depth) arm using a number generator in REDCap. If the number is .0000 to .4999, the individual will be assigned to the intervention condition. If the number is .5000 to .9999, the individual will be assigned to the control condition.

The participant is considered enrolled in the pilot study when they sign a consent form and are randomized to either the intervention or control arm.

F.3 Cytology Sampling

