The cytology sampling will occur immediately after randomization. In preparation, staff will have created two cytology collection kits (labeled as Kit A or Kit B) each containing swabbing instructions, a swab, ThinPrep vial, and gloves. Kit A and Kit B will have identical contents except that Kit A will have a swab with a colored mark 5 cm from the swab tip and Kit B will have a swab with a colored mark 3 cm from the swab tip.

Clinical staff will review the sampling instructions with the individual and then show them to a bathroom in Curative with a locking door where they will do the self-sampling with sampling instructions available. Individuals will be instructed to take the cap off the vial, put on gloves, remove the swab from the packaging, hold the swab at the marker on the shaft of the swab (which corresponds to either 3 cm or 5 cm), get in a comfortable position, insert the swab gently all the way to the mark, begin to twirl the swab clockwise and counterclockwise, and apply pressure to the anal canal walls, while removing the swab as they count slowly to 10.

[figure not shown]

Figure 1. Pilot study schema.

After swabbing, the participant will put the swab in 20 mL of PreservCyt® solution, agitate and twirl it in the solution for 10 seconds, and then remove the swab while pressing against the sides of the vial. The swab will be discarded, the vial cap replaced, and the vial inserted back into the Kit and returned to the staff member. Participants will be instructed to wash their hands.

Participants will complete a short CASI in the consenting office in private on their phone (or hard copy if they prefer) immediately after their self-sampling to assess the swabbing experience, including discomfort and pain, using validated questions. Clinic staff will assist individuals with technology limitations. Participants will then receive \$40.

For those who do not show up for their consenting and cytology appointment, a member of the study team will contact them twice to reschedule within 2 months of their original appointment date.

F.4 Kit Processing, Cytopathology, and Genotyping

Staff will walk the cytology kit to the MCW Tissue Bank who will process the PreservCyt liquid by removing a 0.5 mL aliquot for HPV genotyping. The remaining specimen will be kept in the original vial for cytopathology.

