1. A comparison of the proportions of individuals who collect squamocolumnar cells when using a NF swab with a 5 cm vs. a 3 cm insertion depth.
2. A comparison of the proportions of individuals who collect cytologically adequate specimens when using a NF swab with a 5 cm vs. a 3 cm insertion depth.
3. A comparison of the proportions of individuals who collect adequate specimens for molecular genotyping when using the new NF swab vs. the original swab used in the PAC Self-Swab Study.
4. A comparison of the acceptability and pain performance of the new NF swab vs. the original swab.

H.2 Power for Endpoints

This pilot feasibility study does not have the power to make conclusive statements about the study endpoints.

H.3 Analysis Plan

H.3.1 Preliminary analyses

We will assess the success of randomization. For surveys, we will calculate item response rates for each arm of the study and for subgroups based on HIV status, race/ethnicity, and education.⁴³

After evaluating missing survey data, we will use multiple imputation⁴⁴ to maintain the maximum sample size if data are missing at random. Sensitivity analyses will compare results if data are not missing at random.⁴⁵

In each study arm, we will analyze frequencies of survey items, demographics, other domains, adverse events, and serious adverse events.

H.3.2 Primary Endpoint 1

The presence of cells from the squamocolumnar junction will be assessed in each specimen (Yes/No). Proportions of specimens with squamocolumnar cells will be compared for the 5 cm and 3 cm swabs.

H.3.3 Primary Endpoint 2

Cytologic adequacy is defined as the presence of ~2000-3000 nucleated squamous cells. Proportions of adequate specimens will be compared for the 5 cm and 3 cm swabs.

H.3.4 Primary Endpoint 3

The PAC Self-Swab Study molecular adequacy estimates, given study size, were quite precise with narrow confidence limits. The estimates derived from this pilot study will have wider confidence limits. The original and new swabs will be considered to have commensurate molecular adequacy if the exact confidence limits of the original PAC Self-Swab Study swab are covered by the exact confidence limits of the piloted swab.

H.3.5 Primary Endpoint 4

Each participant will receive a short cytology CASI immediately after the cytology screening to rate their acceptability of the cytology screening on a Likert scale and pain on a visual scale.³⁷ Proportions of individuals' ratings for adequacy and pain will be compared for

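### Do endpoints 1 and 2 need a stated denominator, given that they are worded per individual, per swab and per specimen?

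*Combined protocol and SAP*

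**What the plan says.** Three units appear for the same two endpoints.

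- **Individuals.** The summary, B.2 and H.1 speak of the proportion of individuals who collect the cells, or an adequate specimen, when using the swab.
- **Swabs.** Hypothesis H1 in section A reads "A higher proportion of the new NF swabs with 5 cm insertion will have SCJ cells", and H2 follows the same form.
- **Specimens.** H.3.2 has each specimen assessed as yes or no for squamocolumnar cells, then states "Proportions of specimens with squamocolumnar cells will be compared for the 5 cm and 3 cm swabs". H.3.3 compares proportions of adequate specimens.

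The rules on who counts lie elsewhere. Under F.2 a person is enrolled once consented and randomised. F.3 adds "The cytology sampling will occur immediately after randomization". F.5.3 says "Individuals who sign the informed consent form and are randomized, but subsequently withdraw, will be replaced", and that data already collected from such people are used. F.6 says "An individual is considered to have completed the study if they have completed the post-cytology survey", and G.2 note 3 says "The cytology CASI will be given to participants immediately after they complete cytology collection". The imputation plan in H.3.1 is introduced for missing survey data, not for a missing specimen.

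**The concern.** When one endpoint carries three units and no analysis set is named, the usual worry is that the denominator gets picked once the results are in, and that a reader cannot tell which was used. Here the worry has a plausible mechanism. Section A itself allows that deeper insertion may be less acceptable, so abandoned sampling could be commoner in the 5 cm arm. A proportion taken over vials received would leave those failures out; a proportion over people would count them against the deeper insertion.

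The completion rule seems to widen the gap. F.6 ties completion to the survey rather than to a vial. A person who swabbed, returned nothing and filled in the survey could count as complete, would not have withdrawn, and so would not be replaced. What is at stake is the 5 cm versus 3 cm comparison, which K.5.2 says will inform the choice of swab for the parent study.

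**Working it through.** **Step 1: who separates the three wordings?** Each person gives one swab and one vial, so the units can differ only for people with no vial.

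| Situation | Individual wording (B.2, H.1) | Specimen wording (H.3.2, H.3.3) | Replaced? |
|---|---|---|---|
| Leaves before swabbing | Out: no swab was used | Out: no specimen | Yes, if withdrawn (F.5.3) |
| Uses the swab, returns no vial | In, as a failure | Out | Only if withdrawn, for instance for noncompliance (F.5.2) |
| Uses the swab, returns the vial | In | In | Not applicable |

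Only the second row divides them. It lies off the path in F.3, where the participant puts the swab in the vial, recaps it and returns the kit to staff before doing the survey. G.2 note 3 places the survey after collection is complete and does not say that someone without a vial receives it.

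F.4 adds no rival denominator. The line "specimens will be batched shipped only after all 60 individuals complete the screening" only times the shipment of the genotyping aliquots.

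**Step 2: how much could it move the result?** The plan has no figure to reproduce, because it gives no yield, non-return rate or power.

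Inputs:
- 60 randomised (section D).
- Unrestricted allocation from F.2: "If the number is .0000 to .4999, the individual will be assigned to the intervention condition".
- Assumed yields per specimen of 80% at 5 cm and 70% at 3 cm.
- Assumed one or two people without a vial, not replaced.

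Arm sizes follow Binomial(60, 0.5). P(30/30) = 0.103 and P(23 to 37 in an arm) = 0.948, so splits of 30/30, 23/37 and 37/23 are used.

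Let n5 and n3 be the numbers randomised, and k5 and k3 the numbers with no vial. If no vial counts as a failure, the expected difference is

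0.80 × (n5 − k5)/n5 − 0.70 × (n3 − k3)/n3.

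Example with 30/30 and k5 = 1: 0.80 × 29/30 − 0.70 = 0.773 − 0.700 = +7.3 points, against +10 per specimen.

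The 95% margin with no losses is 1.96 × √(0.16/n5 + 0.21/n3). For 30/30 this is 1.96 × √0.01233 = 21.8 points.

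| Split (5 cm/3 cm) | k5=1 | k5=2 | k3=1 | k3=2 | One each | 95% margin |
|---|---|---|---|---|---|---|
| 30/30 | +7.3 | +4.7 | +12.3 | +14.7 | +9.7 | 21.8 |
| 23/37 | +6.5 | +3.0 | +11.9 | +13.8 | +8.4 | 22.0 |
| 37/23 | +7.8 | +5.7 | +13.0 | +16.1 | +10.9 | 22.7 |

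The largest shift is 10.0 − 3.0 = 7.0 points, about a third of its margin (7.0/22.0 = 0.32). With no losses the denominators agree exactly. If everyone randomised uses the swab, the same figures hold for a denominator of swab users.

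**The case for a change.** The strongest reply is that H.1 and H.3.2 sit in the same section, nothing ranks one above the other, and the sign of a close comparison can depend on the choice. With 30 per arm and two missing vials at 5 cm, 23/28 = 82.1% against 24/30 = 80.0% gives +2.1 points per specimen, while 23/30 = 76.7% against 80.0% gives −3.3 per person. Heavier one-sided loss does more. With 24 positives at 5 cm, 21/30 at 3 cm and five missing vials at 5 cm, the difference is 24/25 − 21/30 = 26.0 points per specimen (Fisher p = 0.015), against 24/30 − 21/30 = 10.0 points per person (p = 0.55).

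The arithmetic stands, and so does the observation that the wording is uneven. Two things limit its force. The sign change is between two differences near zero, with a margin of 1.96 × √(0.821 × 0.179/28 + 0.80 × 0.20/30) = 20 points, so neither supports a preference for a depth. The five-vial example needs one person in six (5/30) at 5 cm to swab on site and hand back nothing, none of them replaced, and nothing in the documents suggests that. Loss on that scale would also show: section L has the team track entry, completed self-sampling, dropouts and reasons every week, although it does not say by arm.

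Nor is the choice as open as it looks. Switching to all randomised people would depart from H.3.2, and no section names that denominator.

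**Conclusion.** No change follows. The endpoints are worded inconsistently, but the section that governs the analysis uses specimens, and that is the right base for a question about what a swab collects. An all-randomised version would mix cell yield with willingness to finish the procedure, so it would not be a better main measure. An analyst following H.3.2 and H.3.3 would count vials received by assigned depth and report the numbers randomised and sampled beside them. Bringing B.2 and H.1 into line would be tidy but would alter no planned result.

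Under the assumed yields and one or two missing vials in one arm, the choice is worth about 2 to 7 points against a margin of about 22. It is worth nothing if every swab user returns a vial. H.2 already disclaims conclusive statements, and no test or decision rule is attached to endpoints 1 and 2.

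This rests on non-return being rare, which on-site sampling makes likely but the documents do not quantify. It also rests on the readable text: Figure 1 and a figure beside F.5.3 are not shown. Many missing vials in one arm would matter, but as a finding about that insertion depth to be reported in its own right.
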